## **1.0 BACKGROUND AND HYPOTHESIS**

We are interested in evaluating a multifaceted prevention protocol for ICU delirium. Delirium affects 45-80% of elderly ICU patients, 60-80% of mechanically ventilated ICU patients, and 20-50% of non-mechanically ventilated ICU patients (1-4). About 30-40% of cases are preventable (1, 2). Without routine screening, delirium is often undiagnosed (5-7). Numerous studies have consistently shown that ICU delirium is associated with a worse prognosis (8). The annual cost of delirium and its ramifications in the U.S., is estimated to be \$4-16 billion (1).

Delirium impacts emotional well-being, as delirious patients experienced delusional memories and had less factual recall than non-delirious patients (9-11). A meta-analysis performed by Zhang et al. found delirium to be associated with a higher mortality rate, longer ICU and hospital lengths of stay, longer duration of mechanical ventilation, and higher probability of discharge to a skilled placement facility. (9) ICU-acquired delirium is independently associated with increased cognitive and physical impairment and health care costs (6, 12). Delirium was also found to be associated with more complications (9,13). Patients who develop delirium have a 2-3 times increased risk of dying during ICU admission (8, 14), with ICU mortality ranging from 1-16% (15-17), and an in-hospital mortality rate of 25% to 33%. (12, 18). It is also associated with increased hospital length of stay (13, 19) and each additional day of delirium increases post-discharge mortality up to a year after discharge (14, 16, 19).

Patients with ICU delirium had a higher incidence of cognitive impairment at hospital discharge, and up to 18 months post-discharge (20, 21) A longer duration of delirium in the hospital was associated with worse global cognition and executive function scores at 3 and 12 months (22), and it is associated with the development of new-onset dementia, or worsening of existing dementia (2, 22). In addition to cognitive problems, delirium was found to be associated with more problems in activities of daily living and worse scores on sensorimotor function tests at follow-up (3). Anxiety, depression, and posttraumatic stress disorder are common in survivors of critical illness (20, 21).

Recent studies evaluating interventions to prevent delirium have focused on “care bundles”, which are comprised of several care procedures incorporated into routine clinical care, that improve patient outcomes. “Bundling” therapies used in the prevention of sepsis, ventilator-associated pneumonia, and central line infections have demonstrated improved clinical outcomes (12). The ABCDEF bundle (daily awakening and breathing coordination trials, delirium monitoring and treatment, early mobility, and family involvement), a multidisciplinary and multicomponent intervention strategy, is increasingly being used in ICUs to decrease length of stay, mechanical ventilation time, complications, and improve outcomes (23). The purpose is to minimize exposure to sedating medications and facilitate early extubation and mobilization (23). It has also been evaluated in the prevention and treatment of delirium and found to decrease delirium incidence and duration, mortality, mechanical ventilator days, hospital length of stay, and improve functional status and overall outcomes (12).

Psychiatric interventions have been evaluated in trauma patients (24), post-CABG patients who develop a psychiatric disorder postoperatively (25) post-intensive care syndrome (PICS) patients (26), and inpatients with delirium (27, 28) and were shown to have beneficial effects. The role of psychiatric interventions in the ICU has not been extensively studied. There are only 3 studies which evaluated the role of psychiatry in the ICU aimed at: 1. minimizing PTSD/anxiety/depression incidence in ICU patients (29), 2. providing a support system for ICU patients (30), and 3. improving the mental health

of ICU patients (31). Additionally, the presence of a psychiatry team rounding with a medical ICU team on nursing and resident education improvement was examined (32). No studies have evaluated the role of psychiatry rounding with the ICU team to prevent delirium and improve long-term outcomes.

The aim of our study is to determine the effect of delirium prevention care bundle protocols and a multi-disciplinary care model rounding with a psychiatry team (intervention group) on the incidence of delirium as compared to a group undergoing standard care without psychiatry participating in ICU rounds (control group). The psychiatric intervention entails a multidisciplinary approach to patient care during rounds, working with the ICU team to make recommendations on non-pharmacological and pharmacological prevention and treatment strategies for patients who are positive for delirium, and helping to differentiate delirium from other psychiatric conditions, that the ICU team may not have the training background to easily identify. Since the incidence of ICU delirium is so high and it has negative ramifications on patient survival, long-term outcomes, cognitive function, and places a heavy burden on the healthcare system and cost, preventative strategies are desperately needed. Using bundle care protocols and multidisciplinary rounding with psychiatry may be a feasible and cheap measure to help prevent delirium in ICU patients.

## **2.0 OBJECTIVES AND PURPOSE**

The purpose of our study is to determine the effect of delirium prevention care bundle protocols, and a multi-disciplinary care model rounding with a psychiatry team (intervention group) on ICU delirium and patient outcomes as compared to a group undergoing standard care without routine psychiatry team participating in ICU rounds (control group). Since the incidence of ICU delirium is so high and it has negative ramifications on patient survival, long-term outcomes, cognitive function, and places a heavy burden on the healthcare system and cost, preventative strategies are desperately needed. Using bundle care protocols and multidisciplinary rounding with psychiatry may be a feasible and cheap measure to help prevent delirium in ICU patients.

The primary objective is the incidence of ICU delirium.

The secondary objectives are:

- duration of delirium
- ICU and hospital length of stay
- days of mechanical ventilation (if applicable)
- in-hospital mortality

Our primary hypothesis is that the intervention of psychiatry team participation in multidisciplinary ICU rounds with the surgical ICU team will result in a decreased incidence of delirium compared to standard care without routine psychiatry team involvement. Our secondary hypothesis is that psychiatric team participation in multidisciplinary ICU rounds will decrease delirium duration, decrease ICU and hospital length of stay, decrease mechanical ventilation duration, and decrease in-hospital mortality compared to the standard care group.

## **3.0 STUDY DESIGN**

This is a prospective, single institution, controlled, pilot study of patients admitted to the 7W ICU which will compare the incidence and delirium rates among patients undergoing routine care before

intervention (no routine psychiatric involvement) (control group) and patients after the intervention (psychiatry team rounding with the ICU team daily) (intervention group) . Randomization is not possible for this study; although block randomization was considered, it will result in sub-optimal data subject to bias.

A sample size of 104 (52 per group) is targeted based on an *a priori* sample size calculation. Patients will be screened on a daily basis for study eligibility by study personnel and ICU team members, before delirium develops. Patients in both groups will be given an information sheet, verbal consent will be obtained, and the patient's agreement to participate will be documented in the medical record. For patients who are unable to make their own decisions, the information sheet will be given to their designated healthcare decision maker, verbal consent will be obtained, and the healthcare decision maker's agreement will be documented in the medical record.

The control group will receive standard care, including the use of the ABCDEF bundle (Appendix 1) daily, which involves delirium screening using the Confusion Assessment Method-Intensive Care Unit (CAM-ICU) score (Appendix 2), but will not have routine psychiatric involvement in care. The CAM-ICU is performed by the ICU nurses on a daily basis. It consists of several questions that assess patient's mental status, if the change in mental status fluctuates, the sedation score (using Richmond Agitation Sedation Score [RASS]), and the patient's attention span and if disorganized thinking is present by asking several questions. The CAM-ICU can be performed in intubated patients by asking the patient to follow commands with their hands, or squeeze the nurse's hand in response to a question. The CAM-ICU will be done every morning, but may also be repeated later on in the day if the patient's mental status changes from the morning-this will be the same for both the control and intervention group. Enrollment and data collection will continue for as long as it takes to reach the target sample size of 52 patients for this group. We will then provide standard care (including ABCDEF bundle implementation, which is standard practice in 7W ICU) and provide routine psychiatric care, which entails a member of the psychiatric team (attending, resident, and/or fellow) participating in daily (Monday-Friday) multidisciplinary rounds with the ICU team (intervention group); the psychiatry team will help provide nonpharmacological and pharmacological intervention strategies in patients diagnosed with delirium and help distinguish delirium from other psychiatric disorders which may be missed by the ICU team and provide earlier treatment of these conditions. This study phase will continue until the target sample size of 52 patients is reached.

In both the control and intervention groups, delirium will be diagnosed by a positive CAM-ICU score. Both groups will have the CAM-ICU test administered by the patient's nurse on a daily basis (which is standard practice in 7W ICU) in the morning and may be repeated later on in the day if the patient's mental status changes. Data on the incidence of ICU delirium, duration of delirium/mechanical ventilation, in-house mortality, hospital and ICU length of stay will be collected.

Additionally, we will collect the following data: age, gender, body mass index, history of alcohol or substance abuse, admitting diagnosis, dementia, comorbid conditions, admitting Sequential Organ Failure Assessment (SOFA) score, deliriogenic medications used during study enrollment, the interventions/medications used to treat delirium as designated by psychiatry and the ICU team (in intervention group) and the ICU team (control group), and the number of days from ICU admission to study enrollment. We will input data into a secure, password protected, encrypted, electronic database, RedCap.

The data points will be compared between the control and intervention groups (see section 13.0).

Our primary outcome is: incidence of ICU delirium.

The secondary outcomes are: duration of delirium/mechanical ventilation, in-house mortality, and hospital and ICU length of stay.

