## **10.0 CRITERIA FOR EVALUATION AND ENDPOINT DEFINITIONS**

Primary outcome: incidence of delirium, defined by a positive CAM-ICU.

Secondary outcomes: delirium duration, ICU/hospital length of stay, in-hospital mortality, and mechanical ventilation duration.

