## **12. DATA COLLECTION AND MONITORING**

Data which will be collected includes: age, gender, body mass index, history or alcohol or substance abuse, admitting diagnosis, dementia, comorbid conditions, admitting Sequential Organ Failure Assessment (SOFA) score, deliriogenic medications used during study enrollment, the interventions/medications used to treat delirium as designated by psychiatry in conjunction with the ICU team (in intervention group) and the ICU team (control group), and the number of days from ICU admission to study enrollment. Data on the incidence of ICU delirium, duration of delirium/mechanical ventilation, in-house mortality, and length of stay will also be collected.

Data will be collected using RedCap, a password protected website. No patient identifiers will be used. A copy of the information sheet will be provided to the patient and be placed in the patient's chart. We will retain a copy of the information sheet in a double locked storage office.

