**CAM-ICU Worksheet**

Feature 1: Acute Onset or Fluctuating Course		Score	Check here if Present

Is the patient different than his/her baseline mental status? OR Has the patient had any fluctuation in mental status in the past 24 hours as evidenced by fluctuation on a sedation/level of consciousness scale (i.e., RASS/SAS), GCS, or previous delirium assessment?
		Either question Yes →	
Feature 2: Inattention			

Letters Attention Test (See training manual for alternate Pictures)
 
Directions: Say to the patient, "I am going to read you a series of 10 letters. Whenever you hear the letter 'A,' indicate by squeezing my hand." Read letters from the following letter list in a normal tone 3 seconds apart.
 
SAVEAHAAART or CASABLANCA or ABABDADAA
 
Errors are counted when patient fails to squeeze on the letter "A" and when the patient squeezes on any letter other than "A."
		Number of Errors >2 →	
Feature 3: Altered Level of Consciousness			
Present if the Actual RASS score is anything other than alert and calm (zero)		RASS anything other than zero →	
Feature 4: Disorganized Thinking			

Yes/No Questions (See training manual for alternate set of questions)
 
 
1. Will a stone float on water?
 
2. Are there fish in the sea?
 
3. Does one pound weigh more than two pounds?
 
4. Can you use a hammer to pound a nail?
 
 
Errors are counted when the patient incorrectly answers a question.
 
Command Say to patient: "Hold up this many fingers" (Hold 2 fingers in front of patient) "Now do the same thing with the other hand" (Do not repeat number of fingers) *If the patient is unable to move both arms, for 2nd part of command ask patient to "Add one more finger"
 
An error is counted if patient is unable to complete the entire command.
		Combined number of errors >1 →	

Overall CAM-ICU
 
Feature 1 plus 2 and either 3 or 4 present = CAM-ICU positive
		
Criteria Met →
 
CAM-ICU Positive (Delirium Present)
	
		
Criteria Not Met →
 
CAM-ICU Negative (No Delirium)
	

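### RASS and the CAM-ICU features are assessed daily but are not on the data lists, so with the data as listed neither adjustment model can account for drift between phases in mental status at entry

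*Combined protocol and SAP*

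**What the plan says.** Section 10.0 sets the endpoint: "Primary outcome: incidence of delirium, defined by a positive CAM-ICU". Section 3.0 says "The CAM-ICU is performed by the ICU nurses on a daily basis", in both groups, and that it includes "the sedation score (using Richmond Agitation Sedation Score [RASS" as well as fluctuation, attention and disorganised thinking. The Appendix 2 worksheet calls the result positive when Features 1 and 2 are present with either 3 or 4. Any other pattern falls under "Criteria Not Met" and counts as no delirium. RASS alone decides Feature 3: "Present if the Actual RASS score is anything other than alert and calm (zero".

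The section 3.0 data list begins with "age, gender, body mass index, history of alcohol or substance abuse, admitting diagnosis, dementia, comorbid conditions, admitting Sequential Organ Failure Assessment (SOFA) score". It goes on to deliriogenic medications, delirium treatments and days from ICU admission to enrolment. Section 12 repeats this ("admitting Sequential Organ Failure Assessment (SOFA) score, deliriogenic medications used during study enrollment") and adds the outcomes. Neither list names RASS, a CAM-ICU feature or any other mental-status value at entry. Section 9.0 adds basic demographics and the CAM-ICU screen, with findings reported on rounds, but does not say that component results enter the study database.

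The control group is filled first and the intervention group second, without randomisation (sections 3.0 and 6.0). Section 13.0 compares incidence by chi-square and multivariable logistic regression. It adds a propensity-score, inverse-probability-weighted sensitivity analysis. It names no covariates for either model.

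**The concern.** A patient who is CAM-ICU negative at entry may show no features or as many as three. Some negatives need only one more feature to become an event; others need two or three. That starting position is the baseline state of the outcome itself. It is assessed every day, but following the lists as written leaves it out of the dataset.

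In a before/after design, shared eligibility criteria and common bundle care give some comparability. Beyond that, confounding control rests on the two models, and weighting can balance only what has been recorded. If sedation practice, referral mix or screening shifts between phases, the share of near-positive or sedated entrants shifts too, and the difference goes into the estimated effect. Section 13.0 intends that estimate to size a later definitive trial, so the error would carry forward.

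**Working it through.** **1. The plan's own figures.** Inputs from section 13.0: base incidence 40%, effect 25%, 47 analysed per group.

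- Difference, 40% v 15%: SE = sqrt(0.40×0.60/47 + 0.15×0.85/47) = 0.0884. The 95% CI is 25 ± 1.96×8.84 = 25 ± 17.3 points, or 7.7% to 42.3%. This matches the stated 8%-42%.
- Reading the 25% as a relative reduction (40% to 30%) would give -9.2% to 29.2%, so the plan means 25 points.
- Base rate: the exact interval at 40% of 47 is 26.0% to 55.3%, matching 26%-55%.

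The present point leaves these figures unchanged.

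**2. What a negative result can hide.** Four present/absent features give 16 patterns.

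- Positive: {1,2,3}, {1,2,4}, {1,2,3,4}, so 3 patterns. The other 13 are negative.
- Negative and one feature short: {1,2}, {1,3}, {1,4}, {1,3,4}, {2,3}, {2,4}, {2,3,4}, so 7 patterns.
- The number of features is not the distance to a positive result. {1,2} and {3,4} both have two features, but the first needs one more and the second needs two. Feature 3 alone also needs two more.

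These count patterns, not patients. The documents give no frequencies.

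**3. Whether a listed item fills the gap.**

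| Listed item | Limit |
|---|---|
| SOFA | Taken at admission; one entry route in section 5.0 requires more than 48 hours in the ICU |
| Deliriogenic medications | Recorded over study enrolment, so may follow entry |
| Dementia, diagnosis, comorbidities | Do not give arousal or attention on the day of entry |
| Days to enrolment | Timing only |

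**4. Size of drift bias (assumed inputs, not in the documents).** Let q0 and q1 be the shares of near-positive entrants in the control and intervention phases, and RR their risk ratio for delirium. Control incidence is 40% and the true effect is zero.

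Risk in the other entrants: lo = 0.40/(1 - q0 + q0×RR).
Spurious reduction = 0.40 - lo×(1 - q1 + q1×RR).

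Example, 40% v 20% with RR 2: lo = 0.40/1.4 = 0.286. Intervention incidence = 0.286×1.2 = 0.343. Spurious reduction = 5.7 points.

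| q0 v q1 | RR 1.5 | RR 2 | RR 3 |
|---|---|---|---|
| 40% v 30% | 1.7 | 2.9 | 4.4 |
| 40% v 20% | 3.3 | 5.7 | 8.9 |
| 50% v 25% | 4.0 | 6.7 | 10.0 |

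Entries are percentage points. Drift the other way would hide a benefit instead.

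**5. Precision.** Assume a 50% share and a 30-point risk gap (55% v 25%, averaging 40%). R² = 0.30²×0.5×0.5/(0.40×0.60) = 0.094. Applied to the plan's half-width: 17.3×sqrt(1 - 0.094) = 16.5 points.

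**6. Room in the model.** Expected events: 0.40×47 + 0.15×47 = 18.8 + 7.05, or about 26.

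**The case against.** **Chance imbalance is not bias.** With a 50% share and a 30-point gap, the share differs between groups by chance with SD sqrt(2×0.5×0.5/47) = 10.3 points. This moves the crude difference by ±1.96×10.3×0.30 = ±6.1 points. A reader might take that as bias, but it is sampling error already inside the 95% interval. It is also the precision gain seen from the other side: sqrt(0.094) × 19.8 points (the half-width at 40% v 40%) = 6.1. A larger assumed gap does not rescue this reading. At 15% incidence with a 50% share, the gap cannot exceed 30 points (30% v 0%). This objection stands.

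**The precision benefit is small.** A reader might convert R² into extra patients: 94×0.094/(1 - 0.094), about 10. That is a linear-model formula. It suits an adjusted risk difference, not the odds ratio from the planned logistic regression. This stands.

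**Silence is not impossibility.** The assessments are routine, so values may be retrievable from charts. Equally, nothing says that feature-level results are charted. The documents therefore do not support saying that adjustment could never be done; they support saying that it cannot be done with the data as listed.

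**Entry is partly controlled.** Section 5.0 excludes early CAM-ICU positives, delirium on DSM criteria, and encephalopathy and other neurological conditions in which the CAM-ICU cannot be performed. This may remove some near-positive patients, but it does not equalise the rest.

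**Entry values may follow exposure.** The documents do not limit psychiatry rounding to enrolled patients, so enrolment values in the second phase may already reflect it. This stands, and the fix must allow for it.

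**It is only one more covariate.** Section 13.0 names none, which is the wider gap. This item differs from an ordinary candidate because it is the outcome's own baseline state, and once left off the data form it may be hard to recover.

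**Conclusion.** The point holds in a limited form. An already assessed baseline state of the primary outcome is missing from both data lists, so the logistic and propensity models cannot use it as planned. The exposure is to systematic drift between phases: about 1.7 to 10 points of spurious reduction, or 7% to 40% of the planned 25-point difference (1.7/25 and 10/25). Those figures rest wholly on assumed shares and risk ratios with no true effect.

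A reader might infer that drift is known to occur, or that the planned comparison is already biased by a set amount. The documents give no data on sedation or feature prevalence in either phase and support neither inference. The section 13.0 precision calculation is unaffected. For a pilot this is a cheap improvement, not a fatal defect.

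**What to change.** 1. Add to the lists in sections 3.0 and 12: RASS and, where charted, CAM-ICU Features 1-4 from the last assessment at or before enrolment. Values from after enrolment should not be used for adjustment.
2. In section 13.0, prespecify one binary term in both the logistic model and the propensity score: one feature short of a positive CAM-ICU, yes or no. If only RASS is charted, use RASS zero v not zero. That is a weaker stand-in, since Feature 3 alone is two features from positive.
3. Record the first ICU assessment as well, and repeat the adjustment with it as a sensitivity check, because psychiatry rounds may reach second-phase patients before enrolment.

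The cost is a few REDCap fields and one covariate slot in a model with about 26 expected events. No new tests or patients are needed. Before the term is fixed, the sponsor should confirm whether feature-level results are charted or only the overall result.

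### Any positive CAM-ICU counts, including optional repeats by nurses who can see the study phase, and the plan collects nothing to show whether repeat testing was equal in the two phases

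*Combined protocol and SAP*

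**What the plan says.** **Endpoint.** Section 10.0 has: "Primary outcome: incidence of delirium, defined by a positive CAM-ICU". Section 3.0 applies the same rule to both groups: "In both the control and intervention groups, delirium will be diagnosed by a positive CAM-ICU score". Neither place limits the outcome to the morning test, so on a plain reading a positive repeat counts.

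**Testing.** Section 3.0 states: "The CAM-ICU will be done every morning". It adds that the test "may also be repeated later on in the day if the patient's mental status changes from the morning", and continues: "this will be the same for both the control and intervention group". Section 9.0 repeats the arrangement. No objective trigger, minimum or cap is given for repeats.

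**Assessor and design.** "Both groups will have the CAM-ICU test administered by the patient's nurse on a daily basis". Section 3.0 also says "Randomization is not possible for this study". The control phase is filled first (52 patients); psychiatry then joins weekday rounds on the same unit for the next 52. No blinding or independent assessor is described.

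**Data and analysis.** The lists in Sections 3.0 and 12 name neither the number, the time nor the reason of CAM-ICU tests. Section 13.0 compares incidence by chi-square and multivariable logistic regression. Its one sensitivity analysis is propensity-score weighting for the lack of randomization.

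**The concern.** Detected incidence depends on true delirium and on how often patients are tested. If the optional repeat is used more in one phase, that phase will record more positive patients with no difference in true delirium. The nurse who decides whether mental status has changed can see which phase is running. Section 1.0 itself notes that delirium often goes undiagnosed where screening is not routine.

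The propensity analysis does not help. Weighting on patient characteristics balances who is in each phase, not how hard the outcome was looked for. Section 13.0 says the base rate and effect size from this pilot will feed the design of a larger trial, so an ascertainment difference would carry forward unseen.

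**Working it through.** **1. The plan's own figures.** Inputs from Section 13.0: control incidence 40%, reduction 25%, 47 per group.

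- Difference, 40% vs 15%: SE = √[(0.40×0.60 + 0.15×0.85)/47] = 0.0884; 0.25 ± 1.96×0.0884 = 7.7% to 42.3%. This matches the stated 8%–42%, so the 25% is in absolute points. (40% vs 30% would give −9.2% to 29.2%.)
- Base rate 40%, n = 47, exact interval: 26.0% to 55.3%, matching 26%–55%.

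Both reproduce. They describe sampling error only and say nothing about detection.

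**2. What the text fixes and leaves open.** It fixes the instrument, the type of assessor, the morning schedule and the rule for repeats. It leaves open how often the repeat is used, and lists no variable from which that could be found out.

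**3. Size with no true effect.** Let s be incidence on scheduled tests, q the share of the remaining patients who are positive only off schedule, and r the chance that a repeat is done. Observed incidence = s + (1 − s)×q×r, so the spurious difference (intervention minus control) is (1 − s)×q×(r_I − r_C). The documents give none of s, q or r; all are assumptions. With s = 0.32 in both phases:

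| q | r 0.5 vs 0.75 | r 0.5 vs 0.9 | r 0.3 vs 0.9 |
|---|---|---|---|
| 0.05 | 0.9 points | 1.4 | 2.0 |
| 0.10 | 1.7 | 2.7 | 4.1 |
| 0.20 | 3.4 | 5.4 | 8.2 |

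(r is control vs intervention.) Example: 0.68×0.10×(0.9 − 0.3) = 0.041. Swapping the two values of r reverses the sign.

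**4. Size under the planned effect.** Put 40% and 15% on scheduled tests:

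| q | r equal at 0.5 | r 0.3 vs 0.9 | r 0.9 vs 0.3 |
|---|---|---|---|
| 0.05 | 24.4 points | 22.1 | 26.4 |
| 0.10 | 23.8 | 19.2 | 27.9 |
| 0.20 | 22.5 | 13.3 | 30.7 |

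Equal testing already lowers 25 slightly, because more patients in the intervention group remain open to an off-schedule positive. The effect of unequal testing is the gap from the first column: 2 to 9 points, in either direction.

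**5. In patients.** One patient is 1/47 = 2.1 points. The planned rates correspond to about 19 vs 7 events: 25.5 points, Wald interval 8.2 to 42.9. Four extra positives in the intervention phase give 19 vs 11: 8/47 = 17.0 points; SE = √[(0.404×0.596 + 0.234×0.766)/47] = 0.0945; interval −1.5 to 35.5. Zero is then no longer excluded.

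**The case against.** **The rule is declared equal.** Section 3.0 says so directly, with the same trigger and the same kind of assessor in both phases. Nothing in the documents shows that testing will differ. That stands: the point is a possibility the plan cannot check, not a demonstrated imbalance. But an equal rule built on an optional repeat does not ensure equal use.

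**A reader might infer that psychiatry's presence raises vigilance, so the bias would probably hide a benefit.** The documents do not support a direction. Sections 3.0 and 7.0 also give psychiatry the task of separating delirium from other psychiatric disorders, which could lead a change in mental status to be explained otherwise and not retested. Psychiatry rounds on weekdays only, and no text gives it a part in prompting later repeats.

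**A reader might also infer a large effect.** Suppose, by assumption, morning tests find 34% of controls and repeats add 6 points. If repeats would add the same 6 points in an intervention group at 30%, doubling that yield shrinks a 10-point reduction to 4. That holds the yield fixed although incidence is lower. If yield scales with incidence, 30% splits into 25.5 + 4.5; doubling gives 25.5 + 9 = 34.5%, a difference of 5.5. For the planned 15%, the split is 12.75 + 2.25; doubling gives 17.25%, a difference of 22.75. That shift of 2.25 points is about one patient in 47, against an interval half-width of about 17 points.

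**Repeat-only positives may be few.** A repeat matters only if the patient is never positive on a morning test, and Feature 1 in Appendix 2 looks back 24 hours. Inattention must still be present the next morning, so this reduces the problem without removing it.

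**Morning-only incidence is not a clean remedy.** Feature 1 can draw on earlier delirium assessments, so repeats feed into the next morning's score. The same nurses score it. A case found in the afternoon and treated before morning would be dropped, perhaps unequally. All of this stands, and it limits that analysis to a supporting role.

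**Conclusion.** The point holds as a gap in ascertainment. Any positive CAM-ICU counts, repeats are optional, phase is visible to the assessor, and no planned data item or analysis would reveal unequal testing. That repeats count, and that nurses know the phase, are inferences from the unrestricted definition and the sequential design; both are close to certain.

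The bias could hide or exaggerate an effect. With no true effect, its size is about 1 to 3 points in mild scenarios (q up to 0.10, r of 0.5 in one phase against 0.25 to 0.9 in the other) and about 8 in the strongest one run. All of these rest on assumed q and r. No stated sample size or interval changes, and in a pilot the mild end is small beside sampling error. It deserves correction because it is cheap to check and because the estimates are meant for planning a later trial.

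**What to change.** Keep any positive CAM-ICU as the primary outcome.

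- **Section 12:** record each CAM-ICU's date, time, result and a scheduled or unscheduled flag, in both phases.
- **Section 13:** pre-specify, by phase, CAM-ICU tests per patient-day and the number of patients positive only on unscheduled tests. These should lead, since they show directly whether detection was comparable. Add incidence from scheduled morning tests only as a supportive sensitivity analysis, and state its limits: it misses some fluctuating or treated delirium, is not fully independent of repeat testing, and does not remove bias from scoring with knowledge of the phase. It does not replace the primary analysis.

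The cost is slightly more data entry and one extra analysis, with no added patients, tests or assessors and no change to care. Recording should cover the control phase as it runs, because test timing may not be reliably recoverable afterwards.
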